3 OBJECTIVES AND ENDPOINTS

OBJECTIVES	ENDPOINTS	JUSTIFICATION FOR ENDPOINTS	PUTATIVE MECHANISMS OF ACTION
Primary			
Test whether continuous theta-bursts stimulation induces sub-critical dynamics in the cortex	Diminished markers of critical dynamics include reduced long-range temporal correlations measured by detrended fluctuation analysis, and sub-critical avalanche branching ratios.	Long-range temporal correlations and avalanche branching dynamics are widely used metrics of distance from the critical point (degree of sub-criticality) in EEG studies.	Long-range temporal correlations and avalanche branching ratios of 1.0 are emergent properties of dynamical systems at a critical point. By reducing the E/I balance, continuous theta burst stimulation should make the brain more sub-critical, thus dampening these emergent properties.
Test whether continuous theta-bursts stimulation to dlPFC diminishes working memory function relative to stimulation to the angular gyrus.	Lower discrimination (d') accuracy and slower reaction times on the N-back following dlPFC stimulation.	Criticality affords dynamic flexibility as needed for rapid, reliable updating in the N-back task, and also flexible task switching. Prior work has shown that dlPFC continuous theta burst can undermine working memory function. Here we test the specific hypothesis that this reflects the effects	A decrease in the E/I balance in the dlPFC produced by dlPFC theta-burst stimulation should make the brain more sub-critical, thus impairing functional flexibility afforded by a critical state. This should matter most

OBJECTIVES	ENDPOINTS	JUSTIFICATION FOR ENDPOINTS	PUTATIVE MECHANISMS OF ACTION
		of TMS-induced sub-criticality in the dlPFC.	in the dlPFC which is a key nexus of higher-order working memory function.
Test whether continuous theta burst stimulation to the dlPFC increases subjective cognitive effort relative to stimulation to the angular gyrus.	Steeper discounting of rewards contingent on the expenditure of cognitive effort following dlPFC stimulation versus angular gyrus stimulation.	By virtue of dlPFC's involvement in working memory and cognitive control, it is hypothesized to play a key role in subjective cognitive effort. We specifically predict that critical dynamics in the dlPFC are what the brain tracks as subjective effort.	
Secondary			

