Test whether continuous theta-burst stimulation decreases E/I balance	Decrease in the functional E/I (fE/I) balance ratio at rest, estimated from EEG data after TMS	The fE/I measure derived from EEG activity has been shown to index E/I balance in silico, and in vivo with humans taking GABAergic medication. Thus, in principle, a change in E/I balance induced by TMS should also be apparent in the EEG dynamics and thereby the fE/I of channels near the stimulation site. Changes in fE/I should moderate effects of theta-burst stimulation on critical dynamics and	Theta-burst stimulation is thought to promote inhibitory neurotransmission, at diverse timescales, thus decreasing E/I balance in local microcircuits. The fE/I measure should be sensitive to these neuromodulatory changes.
Control for session order effects on task performance, subjective effort.	Effects of session order on accuracy (d') and reaction times in working memory task, on	Session order will be included as a covariate in all analyses since participants improve discrimination accuracy and response	Practice improves performance, and people find tasks with which they have more practice

OBJECTIVES	ENDPOINTS	JUSTIFICATION FOR ENDPOINTS	PUTATIVE MECHANISMS OF ACTION
	discounting of rewards as a function of subjective effort.	speed across sessions with the working memory task. In turn, they find tasks to be less effortful across sessions.	to be subjectively easier.
Tertiary/Exploratory			

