4 STUDY DESIGN

4.1 OVERALL DESIGN

The hypothesis to be studied in this Trial is that criticality in the brain depends on the balance of cortical excitation to inhibition and that sub-criticality impacts on working memory and subjective cognitive effort. This hypothesis leads to predictions including that TMS protocols which decrease the cortical excitation to inhibition ratio (like theta burst stimulation) will make the brain more sub-critical. In turn, when theta-burst stimulation is targeted at regions involved in working memory like the dorsolateral prefrontal cortex, this predicts worse, more inflexible working memory performance and greater subjective effort when people are engaged in working memory tasks.

We will use a repeated measures design wherein every subject is their own control. Specifically, on different days, separated by at least one week, participants will receive continuous theta burst stimulation to either their dorsolateral prefrontal cortex (the active condition) or the angular gyrus (the control condition). The order of these sessions is pseudo-randomized across participants. Specifically, 15 of our target 30 participants will be randomly pre-assigned to complete an active condition session first and control condition second and vice versa for the other 15 participants. The pre-assignment will be determined by permutation of a list of subject numbers before recruitment starts. Every subject number will subsequently be assigned to participants in order of their recruitment. Errors in randomization will be documented and session order will be included as a covariate in all analyses.

Participants will come in for three sessions: 1) a first session to complete paperwork and an MRI structural scan for subsequent neuronavigation and a resting state scan, 2) one counterbalanced order session for dorsolateral prefrontal cortex stimulation and working memory task performance and 3) another counterbalanced order session for angular gyrus stimulation and working memory task performance. The first stimulation session can happen the day after an MR scan (but no more than 113 days after the MR

scan) and the second stimulation session can happen one week after the first stimulation session (but no more than 113 days after the first stimulation session).

This is a single-site trial.

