6.3 MEASURES TO MINIMIZE BIAS: RANDOMIZATION AND BLINDING

All participants will complete both one target and one control stimulation session, but the order of these sessions will be pseudo-randomized. Specifically, participants will be assigned participant ID numbers based on their order of recruitment, but the participant ID numbers will be pseudo-randomized with respect to the order of target versus control stimulation sessions. Pseudo-randomization of IDs will be saved in a digital file and included in all subsequent analyses as a covariate of no interest. Any breaking of pseudo-randomization will be corrected with subsequent re-pseudo-randomization of unassigned ID numbers to ensure balance in session orders across participants. This pseudo-randomization will be managed / maintained by the PI.

The specific session that a participant is in (target versus control region) will be known to the experimenter (there is no way for the experimenter not to know since they are administering stimulation). To mitigate the impact on participants, they will be instructed that we will stimulate the brain on two different days, making no reference to possible differential effects across brain regions. The experimental condition will not be explained to the participant until the end of their participation, during debriefing.

Any instance of accidental unblinding – e.g. the participant learns that dlPFC stimulation is considered target, and angular gyrus is considered control stimulation will be noted and subsequent analysis will be conducted both including and excluding these participants to ensure that their inclusion has no effect on the conclusions of the study.

While it may be possible for some participants to infer that effects of stimulation at different sites should have differential effects, they will not be made aware which sites we expect to impact on working memory performance or subjective effort.

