9 STATISTICAL CONSIDERATIONS

There will not be a formal Statistical Analysis Plan (SAP). Also, no statistical plan will be posted publicly or registered before the study begins.

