9.2 SAMPLE SIZE DETERMINATION

While studies on the effects of continuous theta-burst stimulation (cTBS) on critical dynamics have never been conducted, power calculations are based on prior work showing that cTBS can alter E/I balance and working memory function. Specifically, Schicktanz et al. (2015) found that a single train of cTBS to the left dorsolateral prefrontal cortex reduced N-back task accuracy (the same working memory task we will use in the present study) with an effect size on accuracy of $d = 1.39$, 3–21 minutes post-stimulation. This performance effect was established for the 2-back which is our mid-difficulty level. Using g*Power (Faul et al., 2007), we estimate that if the true effect size remains the same, we will have a 95% chance of detecting a cTBS effect on 2-back performance with 30 participants at $p < 0.05$. Importantly, with 30 participants, we will still have 80% power to detect a group difference in performance even if the true

effect size is less than half as large ($d = 0.53$). As such, our target recruitment is set at 30 participants (but will run additional to reach 30 complete participant-session sets, as needed, due to drop-out).

While effect sizes can vary in cTBS owing to considerable inter-individual differences in response to stimulation, we are taking additional measures to reduce reliability including participant-specific brain images and neuronavigation, and also the use of two, rather than one train of cTBS. As such, if anything, we expect the prior estimates to be a lower bound on what we observe.

While this estimate is based on working memory performance alone, this outcome is arguably the most important because it is the one measure that has been linked with E/I balance, with subjective effort, and with critical dynamics in other studies. As such, this measure was selected because it is also informative about all primary and secondary outcomes.

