9.4 STATISTICAL ANALYSES

9.4.1 GENERAL APPROACH

There are no categorical outcomes. Key measures are all continuous outcomes, and are described in detail in the next section. They will be analyzed according to pre- versus post-stimulation means. We will also report standard errors for each outcome. Key outcomes have multiple associated measures. Multiple measures will be used to assess reliability by parallel forms.

We will use standard frequentist cut-offs of $p < 0.05$ for all statistical tests, correcting for multiple comparisons. Key t-tests will include pre-post distinctions in E/I balance measures, working memory performance measures, and measures of criticality.

Covariates of no interest to be included are sex and age which we will incorporate via multiple regression to ask whether cTBS alters key outcomes (described in the next session).

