9.4.2 ANALYSIS OF THE PRIMARY ENDPOINT(S)

The following key outcomes will be assessed in this study. All measures are interval with the exception of the categorical covariate of sex.

- Subjective effort
 - Likert scale ratings (ranging from 1-10) of task-induced effort, demand, time pressure, and stress
 - subjective values as estimated from an indifference point discounting procedure
 - self-reported motivation to engage in demanding tasks on a set of Likert scales with continuous values ranging from 0-20
- E/I balance
 - fEI derived measure with exponents ranging approximately from 0.0-2.0
 - power-law exponents with exponents approximating -2.0
- Critical dynamics
 - Long range temporal correlations – a derived measure with exponents ranging approximately from 0.5-1.0
 - Avalanche size and duration distribution exponents approximating -2.0 and -1.5, respectively
- N-back working memory performance
 - overall accuracy rate as a percentage
 - median correct reaction times by trial type: lures versus targets versus regular trials
 - the discrimination index d'

Primary analyses of these outcomes will entail multiple regression models in which outcomes will be regressed on cTBS condition (target versus sham), controlling for sex and age.

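### The primary regression in section 9.4.2 has no participant effect although every participant contributes both conditions, and it leaves out the session order promised for all analyses

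*Protocol*

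**What the plan says.** Section 4.1 sets up a repeated-measures design: each participant has one dlPFC and one angular gyrus session, and 15 of 30 are assigned to each order. Sections 4.1 to 4.3 justify this by the within-participant comparison and its power.

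Section 9.4.2 then states the primary model for all listed outcomes: "outcomes will be regressed on cTBS condition (target versus sham), controlling for sex and age". Section 9.4.1 gives the same covariates: "Covariates of no interest to be included are sex and age".

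Other sections promise a further covariate. Section 4.1 says that "session order will be included as a covariate in all analyses" and repeats this a few paragraphs later. Section 6.3 says the order assignment will be "included in all subsequent analyses as a covariate of no interest". Section 3 gives the reason: "Session order will be included as a covariate in all analyses since participants improve discrimination accuracy and response" speed from one session to the next.

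Section 9.2 claims that "with 30 participants, we will still have 80% power to detect a group difference in performance even if the true" effect is d = 0.53, and 95% power at d = 1.39. Section 9 rules out a separate plan ("There will not be a formal Statistical Analysis Plan (SAP"), so section 9 is the whole analysis specification.

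**The concern.** There are two faults in the same model statement.

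First, a model with condition as a regressor needs one row per session, so 30 participants give 60 rows in 30 correlated pairs. Nothing in the stated model accounts for the pairing. Sex and age are constant within a participant and cannot stand in for a participant effect. The variance that the crossover was chosen to remove stays in the error term, and the condition effect gets the wrong standard error.

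Second, two covariate sets are given for the same analysis: sex and age in 9.4.1 and 9.4.2, and session order in all analyses elsewhere. Section 4.1 itself calls order effects the main limitation of the design.

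At stake are power and precision at the smaller effect on which section 9.2 relies. In a 30-person mechanistic study, a null result produced by an inefficient model could be read as absence of effect. With no SAP, the choice between paired and unpaired, and order-adjusted and unadjusted, would also stay open after the data are seen.

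**Working it through.** **Inputs.** From the protocol: N = 30 complete pairs, α = 0.05, d = 0.53 with 80% power, d = 1.39 with 95% power, order 15:15. Assumed: two-sided tests; between-session correlation ρ from 0 to 0.9; practice effects of 0.5 and 1.0 SD of the paired difference. The protocol gives neither ρ nor a practice effect.

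**Step 1: reproduce section 9.2 (non-central t).** For a paired test the non-centrality is d√30 on 29 df. With d = 0.53 this is 0.53 × 5.477 = 2.90, and power is 80.1%, matching the stated 80%. For d = 1.39 the paired test gives over 99.9%, not 95%. Two independent groups of 15 have non-centrality 1.39 × √(15 × 15/30) = 3.81 on 28 df and power 95.7%, matching the stated 95%. The same layout at d = 0.53 gives only 28.9%. The two figures therefore fit different designs, and section 9.2 does not show which analysis is meant. The 80% figure needs the pairing.

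**Step 2: standard error of the model as written.** With outcome variance σ² and one row per session, the true variance of the condition contrast is 2σ²(1−ρ)/30. Ordinary least squares without a participant term estimates about 2σ²/30. The ratio of standard errors is about 1/√(1−ρ).

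**Step 3: power.** With the paired standardised effect fixed at 0.53, power is roughly Φ(2.903 − 2.003/√(1−ρ)), where 2.003 is the critical t on 56 df. At ρ = 0.5 this is Φ(2.903 − 2.833) = 53%. Simulation (20,000 trials per setting) gives:

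| ρ (assumed) | Model SE / true SE | Type I error | Power as written | Power, paired |
|---|---|---|---|---|
| 0 | 1.00 | 5.0% | 81% | 80% |
| 0.1 | 1.05 | 4.0% | 78% | 80% |
| 0.2 | 1.11 | 3.1% | 74% | 80% |
| 0.3 | 1.18 | 2.0% | 69% | 80% |
| 0.5 | 1.40 | 0.8% | 54% | 80% |
| 0.7 | 1.79 | 0.1% | 26% | 80% |

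At d = 1.39, taken as the paired standardised effect, the written model keeps at least 99.7% power up to ρ = 0.8 and 87% at ρ = 0.9.

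**Step 4: session order.** In a paired test at d = 0.53 with 15:15 order, an unmodelled practice effect of 0.5 (1.0) SD of the difference cuts power from 80% to 73% (50%). Adding order restores 80%. In the unpaired model at ρ = 0.5 with the 0.5 SD effect, power is 51% without session number and 54% with it, so order matters mainly once the analysis is paired.

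**Step 5: if the order balance slips.** With 15:15 order the omission does not bias the contrast. At an assumed 18:12 split and a practice effect of 0.5 outcome SD, the contrast shifts by 0.5 × 6/30 = 0.1 SD. At ρ = 0.7 the effect is 0.53 × √0.6 = 0.41 SD, so the shift is about a quarter of it. Where the shift opposes the effect, paired power is 42% without order and 79% with it.

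**The case against.** The best defence is that this is silence rather than a wrong model. Sections 4.1 to 4.3 state the within-participant comparison, section 9.3 repeats that the design is within-participant, and the words multiple regression do not exclude a participant term. Likewise, a promise covering all analyses includes 9.4.2, and neither 9.4.1 nor 9.4.2 says that sex and age are the only covariates. The intent is indeed clear. But the model is written out in the one section that defines the primary analysis, it omits both terms, and no SAP is planned to supply them.

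A second defence is reach. Section 9.1 frames the E/I and criticality predictions against pre-stimulation rest, and 9.4.1 assigns pre-post t-tests to E/I balance, working memory and criticality. Those tests are untouched by the point, and change scores could lower ρ; at ρ up to 0.2 the shortfall against the paired test is at most 6 points. This stands in part. However, 9.4.2 applies the regression to every listed outcome, and section 3 defines the effort endpoint as a contrast between sites: "Steeper discounting of rewards contingent on the expenditure of cognitive effort following dlPFC stimulation versus angular gyrus stimulation". Effort discounting is not among the t-tests named.

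Third, the steep fall in power comes partly from holding the paired effect at 0.53 while ρ rises. If the raw effect is held at 0.53 SD instead, the written model has 52%, 53%, 54% and 56% power at ρ of 0, 0.3, 0.5 and 0.7, against 51%, 66%, 80% and 95% for a paired test. So 26% is not a general figure, but the gap still widens with ρ on either scale. Fixing the paired effect is the version that matches the protocol's own 80%.

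Fourth, conservatism depends on having one row per session. Section 9.4.2 lists reaction times by trial type. If k such rows per session are entered together, the written model becomes anti-conservative once (k−1) times the session-level variance exceeds the participant variance. With three rows, simulated type I error ran from 4% to 16% depending on the assumed variances. This strengthens the case for stating the error structure.

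**Conclusion.** The concern holds and should be fixed. As written, the primary model does not use the pairing, and 9.4.1 and 9.4.2 conflict with sections 3, 4.1 and 6.3 on session order. With one row per participant per session and positive ρ, the condition test is conservative: it adds no false positives but loses power at d = 0.53, from almost nothing at ρ near 0 to 26 points at ρ = 0.5 and 54 points at ρ = 0.7. At d = 1.39 the loss is negligible unless ρ is very high. Omitting order is unbiased under 15:15 allocation but costs a paired analysis 7 to 30 points for practice effects of 0.5 to 1.0 SD of the difference. These sizes rest on the assumed ρ, the assumed practice effects and two-sided testing. The direction requires only that a participant's two sessions are positively correlated and that practice effects exist, as section 3 expects.

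**What to change.** In 9.4.2, specify a linear mixed model with condition and session number (1 or 2) as fixed effects and a random participant intercept. Sex and age may stay; they are constant within a participant and do not supply the pairing. Equivalently, regress the paired difference (dlPFC minus angular gyrus) on centred session order and test the intercept. State for each outcome whether the analysed value is the post-stimulation measurement or the pre-post change. Where several rows per session are kept, such as reaction times by trial type, analyse a session-level summary or add a participant-by-session term.

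In 9.4.1, add session order to the covariates so that it agrees with sections 3, 4.1 and 6.3. Code it as session number in the row-per-session model, or as order in the paired-difference model.

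The cost is a rewording of two sections and one degree of freedom. No new data or participants are needed, and power at d = 0.53 with 30 participants stays at 80%.

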9.4.3 ANALYSIS OF THE SECONDARY ENDPOINT(S)

Secondary endpoints will be inter-correlations among the primary endpoint measures. Namely, these correlations will test whether the degree to which cTBS alters one measure correlates with stimulation effects on other measures. Given the large number of possible correlations, we will only test for correlations among those measures which show a reliable stimulation effect in the first place. We will then correct for multiple comparisons among these correlations by the false discovery rate method to control for Type I errors, limiting them to no more than 5% chance.

We will use Pearson's correlations for all tests since our outcome measures are continuous, interval measures.

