The intervention is spaced, continuous theta burst (cTBS) stimulation to either the anatomically-defined dorsolateral prefrontal cortex or angular gyrus. This will entail two trains of 50 Hz triplet bursts of stimulation delivered at 5 Hz (theta rhythm) continuously for 40 seconds (600 pulses for each train for a total of 1200 pulses) at an intensity based on 80% of a participant's active motor threshold. These two trains will be separated by between 5 and 25 minutes of rest, hence the stimulation is "spaced".

Subjects will be their own controls. The use of subjects as their own controls was selected because it will permit within-participant comparisons of the effect of theta burst stimulation on the dorsolateral prefrontal cortex versus the angular gyrus. While this approach will avoid many random individual difference factors which might confound interpretation of effects relative to a between-participants design, the chief limitation of this design is session order effects. Namely every participant will have target stimulation occurring either first, or after a control stimulation session, and they will also perform the working memory tasks either first, or after another session. Session order will be treated as a covariate in all analyses.

The only stratification among participants is gender. There are no expected effects of this stratification.

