9.1 STATISTICAL HYPOTHESES

- Primary Endpoint(s):

We predict that, relative to pre-stimulation rest, continuous theta burst stimulation (cTBS) will result in a reduction of the local balance of cortical excitation to inhibition as reflected in the functional E/I balance in proximity to stimulated targets.

We also predict that, relative to pre-stimulation rest, cTBS will result in a reduction in markers of critical dynamics (including, e.g., long-range temporal correlations) in proximity to stimulation targets.

Finally, we predict that, relative to angular gyrus stimulation, cTBS to the dorsolateral prefrontal cortex will increase subjective cognitive effort.

- Secondary Endpoint(s):

We hypothesize that subjective effort reflects divergence from a critical state and that criticality depends on the E/I balance. As such, we predict that there will be individual difference correlations in the degree to which TMS perturbs E/I balance, alters measures of criticality including long-range temporal correlations, and ultimately amplifies subjective effort.

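### Section 9.4.3 specifies unadjusted Pearson correlations despite the protocol's own session-order rule, which can bias the correlation between performance and effort effects

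*Protocol*

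**What the plan says.** Section 9.4.3 makes the inter-correlations among the primary measures the secondary endpoints: "these correlations will test whether the degree to which cTBS alters one measure correlates with stimulation effects on other measures". It uses Pearson coefficients throughout, on the ground that the measures are continuous and interval. It tests only measures that have already shown a reliable stimulation effect, and it applies a false discovery rate correction. It names no adjustment. The covariates in Sections 9.4.1 and 9.4.2 are sex and age.

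Other sections set a different rule. Section 4.1 says: "Session order will be treated as a covariate in all analyses". The same commitment appears earlier in Section 4.1, in the Section 3 table and in Section 6.3. Section 3 gives the reason: accuracy and speed improve from one session to the next, and "In turn, they find tasks to be less effortful across sessions".

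The design has two stimulation sessions in counterbalanced order: "15 of our target 30 participants will be randomly pre-assigned to complete an active condition session first", and the other 15 have the reverse order. Section 9 states that there will be no formal statistical analysis plan, so no later document is foreseen to settle the matter.

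**The concern.** In a two-session crossover, the difference between the dlPFC and angular gyrus sessions contains the stimulation effect and also the practice gain. The gain is added when the angular gyrus session comes first and subtracted when the dlPFC session comes first. Counterbalancing cancels it from the mean difference. It does not cancel it from the correlation between two differences, because the order groups are shifted apart on both measures.

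Practice raises performance and lowers effort, so the two shifts run in opposite directions. Pooling the groups makes the participants whose performance appears to fall most also appear to have the largest rise in effort, even if no individual responds to stimulation. For reaction time the sign of the coefficient reverses, but the meaning is the same. An analyst who follows Section 9.4.3 literally could report practice as a link between impaired working memory and greater effort. Multiplicity correction does not help, because this is bias and not chance.

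**Working it through.** **Inputs.** From the protocol: 30 participants, 15 per order (Section 4.1); alpha 0.05 (Section 9.4.1; two-sided is assumed, as the protocol does not say); the direction of the practice effects (Section 3). Assumed: the size of the practice effect, which the protocol does not give, so a range is shown.

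**The plan's own figure.** None exists for this point. The nearest is the 80% power at d = 0.53 in Section 9.2. A two-sided paired t-test with n = 30 has noncentrality 0.53 × √30 = 2.90 and power 80.1%, so that figure reproduces. I use 0.53 below as a mean effect.

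**Formula.** Let D be the dlPFC session minus the angular gyrus session, and let p be the practice shift divided by the within-order SD of D. With independent residuals of unit variance, D for performance is shifted by −p1 (dlPFC first) or +p1 (angular gyrus first), and D for effort by +p2 or −p2. With equal groups the covariance is −p1·p2 and the variances are 1 + p1² and 1 + p2², so

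r = −p1·p2 / √[(1 + p1²)(1 + p2²)], which is −p²/(1 + p²) when p1 = p2 = p.

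**Results with no true within-order correlation** (40,000 simulated trials per setting):

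| p on both measures | Expected r | False positives, plain Pearson | False positives, adjusted for order |
|---|---|---|---|
| 0.2 | −0.04/1.04 = −0.04 | 5.4% | 5% |
| 0.3 | −0.09/1.09 = −0.08 | 7% | 5% |
| 0.5 | −0.25/1.25 = −0.20 | 19% | 5% |
| 0.75 | −0.5625/1.5625 = −0.36 | 54% | 5% |
| 1.0 | −1/2 = −0.50 | 88% | 5% |

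For scale, the critical |r| at n = 30 is 0.361.

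**Unequal shifts.** With p1 = 1.0 and p2 = 0.3, r = −0.3/√(2 × 1.09) = −0.20 and the rate is about 20%. With p1 = 1.0 and p2 = 0, r = 0 and the rate is 4.9%. Both measures must shift for the bias to arise.

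**Adding the reliable-effect gate** (taken as both mean differences significant at 0.05, not adjusted for order; re-run with 100,000 trials per setting):

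- No mean stimulation effect: both measures pass and a false correlation is then declared in about 0.02% of trials or fewer. With an order-adjusted gate the figure is at most about 0.2%.
- True mean effect of 0.53 SD on both measures: among trials that pass, the false-positive rate is about 7%, 18%, 52% and 87% at p = 0.3, 0.5, 0.75 and 1.0. Order-adjusted, it is about 5% throughout. As a share of all trials, including those that stop at the gate, the rates are about 4%, 10%, 21% and 22%.

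**The case against.** **Session order is already promised.** Four statements commit to it, and the Pearson sentence can be read as choosing a type of coefficient and not as ruling out adjustment. This largely stands. The plan does not ignore order; it contradicts itself. The specific instruction in Section 9.4.3 still omits the adjustment, and Sections 9.4.1 and 9.4.2 omit it too.

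**The effect may be defined within session.** Section 9.4.1 speaks of pre- versus post-stimulation means and includes working memory performance among its pre-post tests. A constant shift between sessions cancels from a post-minus-pre change. This stands as an ambiguity. Sections 3 and 9.4.2 point to a contrast between sites for working memory, and Sections 3 and 9.1 do so for effort.

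**The gate protects.** It does when there is no mean stimulation effect. Once both measures pass it, the bias is nearly unchanged.

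**A stronger inference to avoid.** A reader might conclude that session order alone would produce the mechanism the trial predicts. The documents do not support that. Section 9.1 says "we predict that there will be individual difference correlations in the degree to which TMS perturbs E/I balance", and it goes on to criticality and subjective effort; N-back performance is not in that prediction. Section 9.1 also defines the E/I and criticality effects against pre-stimulation rest, and the protocol states no session-order effect for the resting EEG measures. On those terms, each correlation in that prediction has at least one measure without a practice shift, and the expected artefact is zero.

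**Conclusion.** The point holds as a contradiction within the protocol, with a bias confined to performance-effort pairs whose effects are differences between sessions. The bias runs toward worse performance with greater effort. It is negligible at a practice shift of about 0.2 within-order SDs, material from about 0.5, and severe at 0.75 to 1.0. The rates of 7% to 88% apply to each test carried out. They assume equal shifts on both measures, 15 participants per order and no true correlation. Since the protocol gives no practice size, it cannot be said where in this range the trial would fall. The mean stimulation contrasts are not affected, and neither, on the protocol's own terms, are the correlations predicted in Section 9.1.

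**What to change.** In Section 9.4.3, specify partial Pearson correlations of the individual effects, adjusted for actual session order (dlPFC first or angular gyrus first). Centring each effect within its order group and testing on 27 degrees of freedom is equivalent. State for each behavioural measure whether the stimulation effect is target minus control or post minus pre. List session order with sex and age in Sections 9.4.1 and 9.4.2, so that they agree with Sections 3, 4.1 and 6.3.

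The cost is one degree of freedom per correlation (28 to 27). The critical |r| rises from 0.361 to 2.052/√(27 + 2.052²) = 0.367. Session order is already recorded, so no new data are needed. One limit should be stated: the adjustment removes the average practice shift, not differences between participants in how much they gain from practice.
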